### **13.6 Statistical Analyses for Exploratory Aim 1 (Age and Race/Ethnicity as Intervention Moderators)**

In the primary analysis described above, we will explore (but do not expect to find) interactions between intervention effects and both age ( $\leq 45$  versus  $> 45$ ) and race/ethnicity (White versus non-White). Based

on pilot data, we estimate that approximately 30% and 25% of the sample will be classified as younger or non-White, respectively. Separate models will be fit for the 2 potential moderators. We will add age/race and interactions between the moderator, intervention, and time point in the regression model described in the Primary Aim. If the 3-way interaction between age/race, intervention, and follow-up time is significant, assessed via a likelihood ratio test, this will provide evidence that the treatment effect significantly differs by age or race. However, interaction effects not meeting statistical significance, but with an estimated magnitude  $> (.5 * \text{main effect})$  will suggest sub-threshold subgroup effects that we will consider in planning next steps including tailoring the IE intervention.

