For interested candidates, screening will determine eligibility and will also include a discussion of study procedures, risks, benefits, and the voluntary nature of their participation, and the fact that it will not affect their medical care if they are a patient at FCCC. Screening the patient for eligibility may occur over the telephone or in person and will include assessment of age, disease status and stage, partner status and age, treatment status and length of time since completing treatment, use of hormone therapy, hearing impairment of patient and partner, current pregnancy, past history of breast or gynecological cancer, current treatment for a concurrent cancer, current participation in marital therapy, and sexual concerns. We used many similar items, including the sexual concerns screening item, in the pilot protocol 15-8007 and have had success with these screening items. Medical record review for all patients will confirm the patients' breast cancer diagnosis, stage, and treatment status, as described in the screening script (or in pre-screening). We will use separate screening scripts for women recruited through site-based versus community-based methods because for women recruited through community-based methods, we will need permission from their clinicians to review their medical records.

Patient eligibility screening will occur privately due to the sensitive nature of the questions and using methods we employed successfully in our R21-funded pilot randomized controlled trial. In order to collect valuable eligibility data about the target population that could be used to inform our development of future studies, all screening items will be administered, and the data will be recorded if patients endorse the item allowing us to keep the information obtained during the screening discussion.

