#### **4.2.3.4 Moderators (Exploratory Aim), Covariates and Other Measures.**

The moderators of patient age and race/ethnicity will be assessed using medical records and pre-treatment self-report survey, respectively. Covariates. Other socio-demographic characteristics (i.e., education, sexual orientation, marital and work status, income, relationship length) will be assessed through self-report. Medical comorbidity for patients and partners will be obtained by a validated self-report comorbidity measure (Self-Administered Comorbidity Questionnaire, SCQ). In order to reduce participant burden and prevent distress, we have modified this measure for patient participants by removing the item asking whether the participant has cancer. We will keep this item for partner participants. Clinical patient characteristics (e.g. menopausal status, comorbidity, types of treatments) will be obtained through medical chart review. Other Measures. We will collect data on frequency of patient sexual activities and use of sexual aids assessed with items from the PROMIS Sexual Function

measure. We also include two items that we developed and assessed in a prior prospective study in colorectal cancer that assess the extent to which sexuality is important to the individual, based on a theoretical model of flexible coping developed by the PI. We are also including the SexFlex Scale, which is a 6-item scale measuring sexual script flexibility when coping with sexual problems. To assess intervention acceptability, at post-treatment (T2), all participants will complete the CSQ-8 and additional questions assessing ease and helpfulness of participation and therapeutic rapport. Based on Borkovec's research, an intervention credibility measure ("Program Evaluation Form") will be completed after session 1 and again at the post-intervention assessment. All participants will complete surveys after session 1, 2, and 3, and again at the post-intervention survey assessing engagement with the material between sessions ("Materials Review Form"). Lastly, we have included a Coronavirus Impact Scale at baseline and six month follow-up to assess the effects the coronavirus pandemic has had on couples' lives, including their relationship and intimacy.

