#### 4.3 Overview of Randomization and Intervention Conditions

Couples will be randomized with an allocation ratio of 1:1 to either the IE or the Educational Control (Living Healthy Together) condition with stratification by age at diagnosis ( $\leq 45$  vs.  $> 45$ ) using the age obtained from the medical record (or by the patient during screening, if age at diagnosis is not available in the medical record). The statistician ([name]) will generate the randomization sequences using an automated randomization procedure in REDCap that limits prediction of allocation and protects masking of allocations. Randomization in blocks of four will guarantee that after every four assignments the study arms will have equal numbers. Separate randomization tables will be used for FCCC, Duke, and community participants to minimize the potential for unequal randomization by site.

Randomization will occur once both members of the couple have consented, completed baseline surveys, and are scheduled for their first intervention session. Randomization will occur centrally at the primary site by a staff member uninvolved in recruitment (to reduce the potential for bias in randomizing participants onto certain conditions). Once randomized, the couple will be sent sealed study materials along with the instructions to leave the envelopes sealed until they “meet” with their interventionist for session 1. It is important to keep the study condition a secret from participants until Session 1 to reduce the chances for unequal drop-out prior to Session 1, which could occur if patients/partners are more motivated to attend sessions in one study group as opposed to the other.

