### **13.8 Power Calculations**

Power calculations are based on Aim 1 (Primary Aim). On the patient sexual function measure, a change of 5 points would be considered clinically meaningful (scale range: 2-36,  $SD \approx 10$ ). Based on pilot data, we anticipate that the  $SD$  of the change scores will be 8.2. Using our prior IE trials to guide attrition estimates, we estimate an attrition rate of 24% at 6-month follow-up, resulting in data available from 92 analyzable couples at 6-month follow-up. We will therefore have 82% power to detect a difference of 5 points in change scores, assuming a 2-sided test with type-I error ( $\alpha$ ) of 0.05. In our breast cancer pilot study, we found a between-groups difference in change scores on patient sexual function of 10.7 at post-treatment. Based on results of similar trials, we expect some attenuation of effects by 6-month follow-up. This study is powered to detect a clinically meaningful change  $> (.5 * \text{main effect})$  through the final assessment point. In sum, the study is conservatively powered to detect an effect of the IE intervention approximately half the size obtained in the pilot trial. The sample size of 120 couples (240 participants) was selected based on these calculations.

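### Age moderation is tested only as 45 or under versus over 45 although age at diagnosis is obtained; if age is roughly normal and the IE effect is linear in age, the split loses about 42% of the information on that interaction

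*Combined protocol and SAP*

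**What the plan says.** Section 2.1 (Exploratory Aim 1) defines the age moderator as age at diagnosis, cut at 45. Section 13.6 repeats the cut and says "we will explore (but do not expect to find) interactions between intervention effects and both age" and race/ethnicity. On the expected split: "we estimate that approximately 30% and 25% of the sample will be classified as younger or non-White, respectively". On the model: "We will add age/race and interactions between the moderator, intervention, and time point in the regression model described in the Primary Aim". The evidence of moderation is a significant three-way interaction of moderator, intervention and follow-up time, judged by a likelihood ratio test. A non-significant interaction whose estimate exceeds half the main effect is still to be considered when deciding how to tailor the intervention.

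The underlying age is available. Section 4.2.3.4: "The moderators of patient age and race/ethnicity will be assessed using medical records and pre-treatment self-report survey, respectively". Section 4.3 stratifies randomisation at the same cut, "using the age obtained from the medical record (or by the patient during screening, if age at diagnosis is not available in the medical record"). Screening under section 4.1.1 "will include assessment of age, disease status and stage".

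The documents give no mean, SD or shape for age, no reason to expect the IE effect to change abruptly at 45, and no power for moderation. The only power figure, in section 13.8, is for the main effect: "82% power to detect a difference of 5 points in change scores".

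**The concern.** A cut at 45 treats patients of 44 and 46 as different and patients of 46 and 75 as alike. That is sensible for a stratification factor, which needs few levels. As a moderator it discards any age trend within each group, so a gradual change in the IE effect is estimated less precisely than the data allow.

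Interactions are estimated imprecisely in a trial sized for a main effect, and here even a non-significant estimate may feed decisions on tailoring. The stake is the precision of an exploratory result.

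**Working it through.** **Inputs.** Share aged 45 or under: 30% (section 13.6). Analysable couples at 6 months: 92, or 46 per arm at 1:1 allocation. SD of change scores: 8.2. Design difference: 5 points. Two-sided alpha: 0.05 (sections 4.3 and 13.8). The shape of the age distribution and the form of the moderation are assumptions, varied below.

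**1. The plan's own figure.** SE of the main effect = 8.2 × √(2/46) = 1.71, and 5/1.71 = 2.92. Power = Φ(2.92 − 1.96) = 83.3% by normal approximation, or 82.5% with a noncentral t on 90 df. The stated 82% is reproduced. Attrition of 24% gives 120 × 0.76 = 91.2 couples, against the stated 92.

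**2. Information kept by the split.** If the IE effect is linear in age, the efficiency of a two-group split relative to continuous age is the squared correlation between age and its indicator. For normal age with share p below the cut, this is φ(z_p)²/[p(1 − p)]. At p = 0.30, z = −0.524 and φ = 0.3477, so the efficiency is 0.3477²/0.21 = 0.576. The loss is 42.4%. On this scale 92 couples are worth 92 × 0.576 ≈ 53.

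**3. Sensitivity of that loss, effect still linear in age.**

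| Age distribution | Share 45 or under | Information lost |
|---|---|---|
| Normal | 30% | 42.4% |
| Normal | 25% | 46.1% |
| Normal | 35% | 39.7% |
| Uniform | 30% | 37.0% |
| Left-skewed (reflected gamma, shape 4) | 30% | 36.1% |
| Bimodal | 30% | 32.4% |
| Right-skewed (gamma, shape 4) | 30% | 55.3% |

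**4. Sensitivity to linearity, normal age.** Information kept, relative to modelling the true shape:

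| True change of IE effect with age | Linear term | Split at 45 |
|---|---|---|
| Linear | 100% | 58% |
| Flat above mean age | 73% | 73% |
| Gradual transition at 45 (logistic, scale 0.5 SD) | 90% | 76% |
| Steep transition at 45 (logistic, scale 0.25 SD) | 78% | 86% |
| Sharp step at 45 | 58% | 100% |

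In these cases the linear term equals or beats the split unless the change near 45 is abrupt.

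**5. Precision at one follow-up (two-way interaction, 92 patients, normal age, linear effect).**
- Split: each arm of 46 has 13.8 younger and 32.2 older patients. SE = 8.2 × √(2/13.8 + 2/32.2) = 3.73 points.
- Linear: SE per SD of age = 2 × 8.2/√92 = 1.71. The group means differ by 0.3477/0.21 = 1.66 SD of age, so the same younger-versus-older contrast has SE 1.71 × 1.656 = 2.83 points.
- Check: (2.83/3.73)² = 0.576, as in step 2.

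**6. What this means for detection.** For an interaction of 2.5 points (half of 5), 2.5/3.73 = 0.67 and 2.5/2.83 = 0.88. Power is about 10% with the split and 14% with linear age. For a 5-point interaction, as large as the main effect the trial is designed to detect, it is about 27% and 42%.

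**7. The half-of-main-effect rule.** Taking the main effect as 5, the marker is 2.5 points. With no true moderation, the estimate exceeds it in absolute size about 50% of the time with the split and about 38% with the linear contrast.

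**The case against.** The analysis is exploratory, uses a cut fixed in advance that matches the stratification, and comes with the authors' statement that they do not expect to find interactions. At the size the plan itself marks as interesting, power is poor under either coding. All of that stands and limits the importance of the point.

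Three stronger readings are tempting, and the documents do not support them.

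- A reader might take 42% as an unconditional loss. It needs roughly normal age and a linear effect, and the documents establish neither. If the effect steps at 45, the split is the better test.
- A reader might take the power figures above as those of the planned test. They describe a two-way interaction on one change score. Section 13.6 tests a three-way interaction by likelihood ratio in the baseline-adjusted repeated-measures model. If moderation is constant over follow-up, that three-way term is zero under either coding, and recoding age gains nothing on the stated criterion.
- A reader might infer that recoding age is the only way to gain power for this aim without more patients. It is not: testing the two-way and three-way terms together would also need no new data. Recoding age does nothing for race/ethnicity, the other moderator.

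Continuous age also complicates the half-of-main-effect rule. That rule works directly for a two-group contrast, but a coefficient per year has no meaning under it until an age contrast is fixed. The fix has to deal with this.

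That the analysis is exploratory does not dispose of the point, because section 13.6 gives the estimate a use in planning, even when it is not significant.

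**Conclusion.** The point holds as a low-cost improvement to an exploratory aim. The plan tests age moderation only as a split at 45, although age at diagnosis is obtained and no reason is given to expect a step there. If age is roughly normal and the IE effect changes linearly with age, the split loses about 42% of the information (about 32% to 55% for the other age shapes tried). It loses nothing under a true step at 45. In the single-follow-up calculation, the contrast has an SE of about 3.7 points with the split against 2.8 with linear age. Continuous age makes the estimate more precise under gradual moderation but does not make the aim well powered. The primary analysis is unaffected.

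**What to change.** In section 13.6, with matching wording in Exploratory Aim 1 (section 2.1):

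- Test age moderation with age at diagnosis as a continuous variable, entered linearly, with a restricted cubic spline as a check on shape.
- Report the estimated IE effect with its confidence interval at stated ages, for example 40, 50 and 60.
- State the fixed age contrast to which the half-of-main-effect rule applies, for example the difference in IE effect between two named ages.
- Keep 45 or under versus over 45 as the stratification factor and as a reported subgroup display.

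The cost is wording in two sections, one added shape check, and agreement on the contrast. No new data are needed. The change should be made before any unmasked analysis. The downside is lower efficiency if moderation is abrupt at 45: with normal age, the linear test keeps 78% of the information against 86% for the split under a steep transition, and 58% against 100% under a perfectly sharp step. Retaining the subgroup display keeps such a pattern visible.

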### 2.1 Specific Aims

**Specific Aim 1 (Primary Aim):** To evaluate whether the IE intervention will lead to a significantly greater increase in patient sexual function from pre-treatment to post-treatment and 3- and 6-month follow-ups compared to the LHT condition.

**Specific Aim 2 (Secondary Aim):** To evaluate whether the IE intervention will lead to significantly greater improvements in (a) partner sexual function and (b) patient and partner relationship intimacy and quality and psychological distress from pre-treatment to post-treatment and at 3- and 6-month follow-ups, compared to the LHT condition.

**Specific Aim 3 (Secondary Aim):** To evaluate whether increases from pre- to post-treatment in patient sexual communication and self-efficacy for coping with sexual concerns mediate the beneficial effects of the IE intervention on patient sexual function at 3- and 6-month follow-ups.

**Exploratory Aim 1:** To explore whether age ( $\leq 45$  versus  $> 45$  at diagnosis) and race/ethnicity (White versus non-White) moderate intervention effects on the primary outcome of patient sexual function.

**Exploratory Aim 2:** To identify participation barriers and intervention preferences of breast cancer survivors who choose not to participate in the Intimacy Enhancement study.

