### **13.2 Statistical Analyses for Aim 1 (Primary Aim; Effects of IE Intervention on Patient Sexual Function)**

The primary analysis will examine whether, relative to the LHT condition, the IE condition leads to greater increases in the primary outcome of patient sexual function at all three post-treatment assessments (T2-4; post-treatment; 3-month FU; 6-month FU). We will also examine specific domains of sexual function (satisfaction, desire, arousal, lubrication, orgasm, pain) separately. In a mixed effects regression model, study condition will serve as the independent variable and patient sexual function at each time point will serve as the dependent variable; pre-treatment sexual function will be included in the model as a covariate with time included as a categorical covariate. Intervention by time interaction effects will be included to test the intervention effect at each follow-up time. Subject-specific random intercepts will account for within-subject variability. Intervention effects on patient sexual function at each follow-up are tested using F tests of combined main and interaction effects.

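### The only significance test for moderation in section 13.6, the 3-way term, cannot detect a subgroup difference that is the same at every follow-up

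*Combined protocol and SAP*

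**What the plan says.** Section 2.1 states Exploratory Aim 1 as whether age and race/ethnicity "moderate intervention effects on the primary outcome of patient sexual function".

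Section 13.6 builds on the primary model: "We will add age/race and interactions between the moderator, intervention, and time point in the regression model described in the Primary Aim". The decision rule begins "If the 3-way interaction between age/race, intervention, and follow-up time is significant, assessed via a likelihood ratio test" and concludes that "this will provide evidence that the treatment effect significantly differs by age or race". No test of the 2-way moderator by intervention term is given. For interactions that are not significant but exceed half the main effect, the section says they "will suggest sub-threshold subgroup effects that we will consider in planning next steps including tailoring the IE intervention".

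The primary model in 13.2 takes patient sexual function at T2, T3 and T4 as the outcome. On baseline and time it says that "pre-treatment sexual function will be included in the model as a covariate with time included as a categorical covariate". Its own test of the intervention is built differently from the one in 13.6: "Intervention effects on patient sexual function at each follow-up are tested using F tests of combined main and interaction effects".

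**The concern.** Because baseline is not an outcome row, the 3-way term has 2 degrees of freedom and compares the subgroup difference in treatment effect between follow-ups. A significant result does imply that the treatment effect differs by subgroup at some follow-up, so the inference in that direction is sound. The reverse fails. If younger women gain more than older women by the same amount at T2, T3 and T4, the 3-way term is zero and the stated test does not see it.

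The test therefore addresses whether moderation drifts over time, while the aim asks whether moderation exists. A non-significant result could be read as support for the plan's expectation of no interaction, when the test could not have found stable moderation. The informal rule might pick up such an effect, but it carries no error rate, does not identify its coefficient, and labels whatever it flags as below threshold. It also feeds decisions about tailoring the intervention.

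**Working it through.** **The plan's own figure.** Section 13.8 gives 82% power for a 5-point difference, change SD 8.2, 92 couples (46 per arm), two-sided alpha 0.05. The noncentrality is 5 / (8.2 × √(2/46)) = 2.92. Power is 83.3% by the normal approximation and 82.5% by the noncentral t with 90 df, so the figure reproduces. No power is stated for 13.6.

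**Inputs.** From 13.8: SD about 10, change SD 8.2, 92 couples. From 13.6: 30% younger, 25% non-White. From 4.3: 1:1 allocation. Assumed: alpha 0.05 for 13.6 (it gives no level), 92 couples at every follow-up (13.8 gives this for 6 months only), and residual correlation r = 0.4 between follow-ups, with range 0.3 to 0.7.

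**Residual variance.** The baseline correlation is 1 − 8.2²/(2 × 10²) = 0.664. The residual variance after baseline adjustment is v = 100 × (1 − 0.664²) = 55.9.

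**Covariance of the subgroup differences.** Let m be the three subgroup differences in treatment effect at T2–T4. Under a random intercept, Cov(m) = v × k × [(1 − r)I + rJ], where k = 2/(np) + 2/(n(1 − p)) and n = 46. For p = 0.30, k = 2/13.8 + 2/32.2 = 0.207, so vk = 11.58. For p = 0.25, k = 0.232.

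**Noncentralities.**
- 3-way (2 df): Σ(m_t − mean)² / (vk(1 − r))
- Average (1 df): 3 × mean² / (vk(1 + 2r))
- Joint (3 df): the sum of the two

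When all m_t are equal, the 3-way numerator is zero whatever v, k and r are. This result needs none of the assumptions above. Two worked cases at p = 0.30, r = 0.4:
- Constant 10 points: joint = 300/(11.58 × 1.8) = 14.4; 3-way = 0.
- 10, 7.5, 5 points: 3-way = 12.5/(11.58 × 0.6) = 1.80; joint = 1.80 + 8.10 = 9.89.

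**Power at r = 0.4.**

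| Difference at T2, T3, T4 | Subgroup share | 3-way | Joint 3 df | Average 1 df |
|---|---|---|---|---|
| 5, 5, 5 | 30% | 5% | 33% | 48% |
| 7.5, 7.5, 7.5 | 30% | 5% | 66% | 81% |
| 10, 10, 10 | 30% | 5% | 91% | 97% |
| 10, 7.5, 5 | 30% | 21% | 76% | 81% |
| 7.5, 5, 2.5 | 30% | 21% | 47% | 48% |
| 10, 5, 0 | 30% | 67% | 80% | 48% |
| 5, 5, 5 | 25% | 5% | 29% | 43% |
| 7.5, 7.5, 7.5 | 25% | 5% | 61% | 77% |
| 10, 7.5, 5 | 25% | 19% | 70% | 77% |
| 10, 5, 0 | 25% | 62% | 74% | 43% |

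Over r = 0.3 to 0.7 with 30% younger, joint power is 25–36% at constant 5 points and 52–72% at constant 7.5. At 10, 7.5, 5 points the 3-way test has 18–38% and the joint test 73–79%.

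**Sensitivity to the variance.** With residual SD 8.2 instead of √55.9, joint power at constant 10 points (30% younger, r = 0.3 to 0.7) is 71–88%. The 3-way test stays at 5%.

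**Simulation.** With 1,000 data sets per case (30% younger, r = 0.4), random-intercept likelihood ratio tests gave these 3-way / joint rejection rates: no moderation 6.1% / 6.3%; constant 7.5 points 5.1% / 64.6%; 10, 7.5, 5 points 21.7% / 78.1%. In a second simulation (SD 8.2, r = 0.5, 92 couples, 10,000 runs), the 3-way test rejected 5.8%, 5.6%, 5.7% and 5.7% at constant differences of 0, 5, 10 and 20 points. The slight excess over 5% is present with no moderation too, and reflects the asymptotic test.

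**Informal rule with no true moderation.** Take 30% younger, r = 0.4 and a main effect fixed at 5 points, so the trigger is 2.5. The SE is √(11.58 × 1.8/3) = 2.64 for the average over T2–T4 and √11.58 = 3.40 at one visit. Then 2 × P(Z > 2.5/SE) is 34% and 46%. With a main effect equal to the pilot's 10.7 points (13.8), the trigger is 5.35 and the rates are 4% and 12%.

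**The case against.** The aim is exploratory, the plan says it does not expect interactions, and 13.8 powers only Aim 1. This stands, and it limits the point to an optional improvement.

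Section 13.8 says "we expect some attenuation of effects by 6-month follow-up". If moderation faded along with the overall effect, the 3-way test would have some power: 18–38% at 10, 7.5, 5 points and about 60–94% at 10, 5, 0 (30% younger, r = 0.3 to 0.7). That is fair. But a fading overall effect need not mean a fading subgroup difference, and under moderate fading the 3-way test remains far below the joint test.

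The authors may have intended a joint test and worded it loosely, since 13.2 already combines main and interaction effects. This is plausible, but 13.6 names only the 3-way term, so the text needs correcting either way.

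The half-of-main-effect rule may catch a large stable difference. It may, without a p-value. Its chance trigger rate depends on the size of the main effect. The 34% and 46% also treat that effect as known and count both directions; one direction alone gives 17% for the average. So the rule is noisy if the main effect is near 5 points and much less so near 10.7.

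Finally, for a strictly constant difference the 1-df average is more powerful than the joint test. That is correct, and choosing between them is partly a matter of judgment.

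**Conclusion.** The concern holds. As written, the only significance test for moderation has power equal to alpha for any subgroup difference that is constant over T2–T4. That follows from the model in 13.2 and does not depend on the SD, correlation or subgroup share. The power figures for the alternatives do depend on them, and on 92 couples being available at each follow-up. On those assumptions the joint test exceeds the 3-way test in every constant and fading pattern computed. Even so, its power for a 5-point subgroup difference is low (25–36% with 30% younger), and it becomes useful only for differences of roughly 7.5 to 10 points. Primary and secondary conclusions are not affected. This is a change to consider, not a threat to the trial.

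**What to change.** In 13.6, for each moderator, test moderation by a likelihood ratio test comparing the full model with one that omits both the moderator by intervention and the moderator by intervention by time terms (3 df). The moderator main effect and moderator by time terms stay in both models. Use the 3-way term only to describe whether moderation changes over time. State which coefficient, and at which visit or average of visits, the half-of-main-effect rule refers to.

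The joint test is preferred to the 1-df average because the average falls below even the existing 3-way test when the difference fades to nothing (48% against 67% at 10, 5, 0 points, 30% younger, r = 0.4). It also matches the combined-effects testing already used in 13.2.

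The cost is one or two sentences, with the same fitted model and the same data.
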